13.13 LCTC Responsibilities

The trial Sponsor, (University of Liverpool) have delegated to LCTC the duty of onward reporting of safety events to REC, regulatory authorities and Sponsor. Standard Operating Procedures (SOPs) will be followed to ensure appropriate reporting as detailed below.

All "serious" safety events will be forwarded to the CI (or delegate) by LCTC within 24 hours of receiving the minimum information from site. The CI (or delegate) will review information provided by site and confirm the appropriate MedDRA code to be used for the event and assess 'relationship' and 'expectedness'.

Safety events which are assessed as "serious", "related" and "unexpected" will be expedited to the REC as applicable for clinical trials and applicable regulators, e.g. MHRA as a SUSAR within the following timeframes:

- SUSARs which are fatal or life-threatening as soon as possible and in any case no later than 7 days after the LCTC is first aware of the event. If the initial report is incomplete, a complete report will be submitted within an additional 8 days.
- SUSARs that are not fatal or life-threatening within 15 days of the LCTC first becoming aware of the event.

Additionally, SUSARs will be reported to the trial Sponsor and PIs of participating sites within the agreed timelines.

The LCTC will submit an Annual Safety Report to REC and a Development Safety Update Report to the MHRA on an annual basis.

The events below are considered for expedited reporting:

- An increase in the rate of occurrence or a qualitative change of an expected SAR, which is judged to be clinically important;
- Post-study SUSARs that occur after the participant has completed a clinical trial and are notified by the investigator to the Sponsor;
- New events related to the conduct of the trial or the development of the IMPs and likely to affect the safety of the participants, such as:
 - A SAE which could be associated with the trial procedures and which could modify the conduct of the trial;
 - A significant hazard to the participant population, such as lack of efficacy of an IMP used for the treatment of a life-threatening disease;
 - A major safety finding from a newly completed animal study (such as carcinogenicity).
 - Any anticipated end or temporary halt of a trial for safety reasons and conducted with the same IMP in another country by the same Sponsor;
 - Recommendations of the IDSMC, if any, where relevant for the safety of the participants.

The PIs at all institutions participating in the trial will be notified of any SUSARs within a reasonable timeline, and if appropriate.

Any concerns raised by the IDSMC or inconsistencies regarding safety reporting noted at a given site may prompt additional training at sites, with the potential for the LCTC to carry out site visits if there is suspicion of unreported AEs / ARs and SARs / SAEs in participant case notes. Additional training will also be provided if there are unacceptable delays in safety reporting timelines.

Urgent Safety Measures (USMs)

An urgent safety measure (USM) is a procedure to protect clinical trial participants from any immediate hazard to their health and safety but has not previously been defined by the protocol. It can be put in place prior to authorisation by the REC and the MHRA.

The LCTC will notify the MHRA and REC immediately and, in any event, within 3 days that such a measure has been taken and the reasons why it has been taken. The initial notification to the REC and MHRA will be by telephone (ideally within 24 hours) and a notice in writing will be sent within 3 days, setting out the reasons for the USM and the plan for further action. After discussion with the REC and MHRA, further action will be agreed, which may include submission of a substantial amendment, a temporary halt, or permanent termination of the trial.

Following notification, if a substantial amendment is required this must be submitted as soon as possible to the REC and ideally within two weeks to the MHRA. If the study is temporarily halted it may not recommence until authorised to do so by the REC and MHRA. If the study is permanently terminated before the date specified for its conclusion (in the original applications to REC and MHRA), the Sponsor should notify the REC and MHRA within 15 days of the date of termination by submitting the formal End of Trial Notification.

13.14 Contact Details and Out-of-hours Medical Cover

As Anakinra has a well-established safety profile, emergency and out-of-hours medical care will be in line with usual NHS arrangements and local standard practice; no special provision is required for INCA participants. All participants will be provided with a contact card and copy of the information sheet which includes information about their participation and contact details for the local research team who may be contacted if necessary. During office hours, the CI or delegate are able to provide medical advice in relation to participation using the contact details listed at the beginning of this document.

14 STATISTICAL CONSIDERATIONS

14.1 Introduction

All baseline, primary and secondary outcome measures will be reported using appropriate summary statistical measures. There are no formal hypotheses evaluated in this study.

14.2 Sample Size

A sample size of 30 has been estimated for this feasibility study. As this is a feasibility study, the sample size calculation can be difficult to determine.

Hertzog 2008 [38] recommends a sample size of between 20 and 40 patients for feasibility studies involving group comparisons. Hertzog suggests 30-40 patients per group will be required to yield confidence intervals whose lower limits can help define the range of plausible values for a subsequent power analysis.

Whitehead et al. 2016 [39] produced methods of calculating the optimal solution and approximate rules. For a main trial designed with 90% power and two-sided 5% significance, Whitehead et al. recommends a feasibility trial sample size per treatment arm of 75, 25, 15 and 10 for standardised effect sizes that are ≤0.1 (extra small), 0.2 (small), 0.5 (medium) and 0.8 (large) respectively.

The results of this feasibility study of 30 patients (single arm) will serve as data for sample size calculations for a further study. There are ethical and economic reasons for keeping this study population small, however the study results need to provide enough information to fulfil the specified primary and secondary endpoints.

With these reasons in mind and the recommendations of the two reference papers above, a sample size of 30 patients will be used for the INCA feasibility study.

The main outcome that will contribute to data for subsequent studies will be based on changes in pain intensity as measured by NRS (see Section 9). Feasibility data regarding the potential effects of Anakinra on pain intensity will be used to inform the sample size for the next stage of the study. The primary outcome of safety (throughout the study) and recruitment will be used to assess the rationale and feasibility of performing a larger RCT.

14.2.1 Feasibility of Sample Size

Between the two recruiting sites we expect a recruitment rate of one patient every month (across the two centres) for the first 6 months from commencing recruitment. In the second 12 months recruitment rate will be expected to be two patients monthly across both sites.

14.3 Interim Analyses

The trial will be assessed at regular intervals (at least annually) by the IDSMC. The IDSMC will be asked to review the conduct of the trial in terms of patient recruitment and safety/toxicity. Assessments of the primary endpoint shall be presented to the IDSMC in terms of the proportion of participants tolerating Anakinra and the safety of Anakinra in participants with refractory moderate to severe CRPS. The IDSMC will be asked to make a recommendation as to whether the study assessments presented at each meeting justify continuation of further patient recruitment and/or remaining follow-ups in accordance with the study protocol and guidelines on progression (as detailed in section 11 of the protocol).

•

14.4 Analysis Plan

A full statistical analysis plan (SAP) will be written prior to the conduct of any statistical analysis of the cohort. The main features of the SAP are summarised below:

14.4.1 Patient Groups for Analysis

Full Analysis Set

In order to follow the Intention To Treat (ITT) principle this will consist of all eligible and registered participants at baseline (0 day), excepting for: a) participants withdrawing consent between baseline (0 day) and starting therapy; b) participants withdrawn from the study after baseline (0 day) because of irregularities with the consent process; c) participants whose information determining ineligibility existed before registration but was not read until after registration.

Safety Set

All participants who received at least one dose of the trial treatment.

14.4.2 Assessment of Study Quality

Study quality will be summarised in terms of withdrawals / losses to follow-up, protocol deviations and extent of missing critical data.

14.4.3 Exposure to Treatment / Compliance

Exposure to treatment will be assessed by mean dose (mg) per participant. Dosing is once daily for a maximum of 120 days; the mean number of doses per participant over the treatment period (expressed as number of days treatment administered for) will be summarised.

Compliance of treatment will be captured by summarising the number of returned used syringes compared to non-used syringes.

14.4.4 Description of baseline (0 day) Patient Characteristics

Participant demographics and baseline (0 day) measures will be summarised appropriately for the cohort.

14.4.5 Missing data

As much information as possible will be collected about the reasons for missing outcome data. Final analyses are planned to be carried out on a complete case basis. Further details will be described in the statistical analysis plan.

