8.5 Treatment Modifications

After the participant has entered the trial, the clinician is free to give alternative treatment / intervention to that specified in the protocol, at any stage, if s/he feels it to be in the best interest of the participant. However, the reason for doing so should be recorded and the participant will remain within the trial for the purpose of follow-up and data analysis according to the treatment option to which they have been allocated. Similarly, the participant remains free to withdraw at any time from the protocol treatment and trial follow-up without giving reasons and without prejudicing further treatment, see section 10.9.

8.5.1 **Dose adjustments**

Anakinra is administered as a fixed dose 100mg subcutaneously once daily for participants whose body weight is 50kg or more, participants with a body weight of less than 50kg will administer 2mg/kg

subcutaneously once daily. The prescribed dose will be calculated and retained from baseline (0 day) to 120 days. No dose modifications will take place beyond the baseline (0 day) visit

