10.9 Intervention Discontinuation and Participant Discontinuation/Withdrawal

In consenting to the trial, participants agree to all trial activities including administration of trial intervention and treatment and follow-up assessments/visits and data collection. Every effort should be made to facilitate the completion of these for every recruited participant. If it is not possible to complete these activities (or it is deemed inappropriate) the reasons why should be documented. The following sub-sections describe the different levels of discontinuation/withdrawal.

Premature Discontinuation of Trial Intervention

Participants may discontinue treatment for reasons including, but not limited to:

- Patient-led i.e. request by the patient / legal representative / consultee
- Unacceptable toxicity (see Section 13 for AE reporting)
- Intercurrent illness preventing further treatment.
- CRPS symptom progression which requires discontinuation of therapy or results in inability to continue to comply with study procedures
- Pregnancy
- Death
- Clinician-led:
 - Any change in the participant's condition that justifies the discontinuation of treatment in the clinician's opinion.
 - Reasons of non-adherence or non-compliance with treatment or other trial procedures
 - Participant meets an exclusion criterion (either newly developed or not previously recognised)
 - Participant unable to receive Anakinra for >=7 days consecutively

Discontinuation from Anakinra does not mean discontinuation of the study altogether, and the remaining study procedures, follow up assessment/visits and data collection should be completed as indicated in the protocol unless the patient requests to withdraw from further follow up visits. Data to be collected at the time of discontinuation will include the following:

- 1. Reason for discontinuation (if available)
- 2. Any AEs
- 3. Pain intensity score (NRS)

If a study participant is discontinued from the study early, an End of treatment CRF will be completed describing the reason for discontinuation. In situations where treatment is withdrawn due to an AE, participants will be followed up until resolution of that AE or determination that the participant's condition is stable. All AEs will be followed up until 180 day.

In case of a Participant Withdrawal the participant will be assessed for AEs, if any, and medication use.

Participant Withdrawal from Follow Up

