#### 22 Analysis Datasets

#### 22.1 Efficacy Analyses

The primary and secondary outcome analyses will be conducted on all registered participants and for whom the outcome(s) of interest have been observed/measured. Patients who withdrew consent for trial continuation will contribute outcome data up until the point of withdrawal unless the patients' specifically request that the data are not to be used. No imputations will be made.

The membership of the analysis set for each outcome will be determined and documented and reasons for participant exclusion will be given prior to analysis. Reasons may include missing data, loss to follow up.

A per protocol analysis will not be performed, instead the occurrence of each protocol deviation will be monitored and sensitivity analysis performed as appropriate with patients experiencing deviations

of concern removed. The sensitivity analysis will apply to a secondary analysis of the primary outcome only.

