#### 25.2.3.2.1.1 Derivation

The total weekly score will be calculated as the total NRS score per week for days 93 to 120 (last 4 weeks, inclusive of days 93 and 120) from the patient pain diaries. The mean of the total weekly scores (average weekly score) per patient will be calculated as:

[sum of total weekly scores for days 93 to 120 (inclusive)]/ 4.

The mean daily average over the last month per patient will be calculated as:

[sum of the scores for days 93 to 120 (inclusive)]/28.

The change in score will be the weekly and daily average at day 120 minus the baseline score. The baseline score is collected on Form 4: Baseline and is the average pain from CRPS over the last 24 hours at baseline.

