#### 25.2.3.2.3.2 Analysis

The number of patients to complete the form will be reported. Categorical data will be summarised using frequencies and percentages at day 120 with the denominator being those who completed the question.

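### The day-120 pain-change summary loses participants with no diary data in days 93–120 and makes no use of their earlier scores, so it may be too favourable and its SD too small if those who left had worsened

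*Protocol*

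**What the plan says.** Protocol 14.4.5 sets the rule for the final analysis, "Final analyses are planned to be carried out on a complete case basis", and leaves the detail to the SAP. SAP 22.1 limits each outcome to registered participants "for whom the outcome(s) of interest have been observed/measured" and adds "No imputations will be made". The one sensitivity analysis it plans concerns protocol deviations in the primary safety outcome.

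SAP 25.2.3.2.1.1 derives the day-120 pain score from one four-week diary window. The daily version is "sum of the scores for days 93 to 120 (inclusive)]/28". No earlier post-baseline score enters the change from baseline.

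Protocol 10.9 gives, among the reasons for stopping the drug, "CRPS symptom progression which requires discontinuation of therapy or results in inability to continue to comply with study procedures". The same section says that stopping anakinra does not end study participation and that remaining assessments go on unless the patient withdraws from follow-up.

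On the use of the result, protocol 14.2 says: "The main outcome that will contribute to data for subsequent studies will be based on changes in pain intensity as measured by NRS".

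Global impression is collected at day 120 only, and SAP 25.2.3.2.3.2 reports its percentages "with the denominator being those who completed the question".

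**The concern.** A complete-case summary describes the people who were still filling in the diary in the last month. That is harmless if leaving has nothing to do with pain. Here the protocol itself names a route by which worsening CRPS could stop someone from continuing study procedures. If that happens before day 93, the participant's worsening is missing from the one outcome that protocol 14.2 singles out for planning the next study.

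The information to do better is already being collected. Section 10.7 of the protocol schedules weekly diary scores to day 90. Table 4 schedules an NRS at every clinic and telephone contact and at premature discontinuation. At stake is the planning of the RCT. This study is descriptive, has no formal hypothesis, and so has no type I error to protect.

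**Working it through.** **1. Who is lost from this outcome**

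| Situation | Days 93–120 value? |
|---|---|
| Stops anakinra, stays in follow-up and keeps the diary | Yes; included |
| Ends follow-up or stops the diary before day 93 | No; excluded |
| Stops the diary between days 93 and 120 | Unclear; the SAP does not say how a partial diary counts |

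The third row matters for defining the group. If a partial diary were summed over the fixed divisor, unrecorded days would count as zero pain. With a constant NRS of 8 and a last entry on day 105 there are 13 entries, and 13 × 8 / 28 = 3.71, an apparent change of 3.71 - 8 = -4.29 with no true change.

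**2. Possible size of the bias**

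The sample of 30 rests on rules of thumb, so there is no planned effect, SD or dropout figure to reproduce. All inputs here are assumptions: true mean change 0, SD 2 NRS points, correlation r between the change seen before leaving and the final change, and 20% missing (24 of 30 remain).

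*The worst fifth on the earlier score leave.* The cut-point is 0.842 SD, and 0.280 / 0.80 = 0.350 is the normal density there divided by the fraction kept.
- Bias in the mean = -r × 2 × 0.350. With r = 0.7 this is -0.49.
- Relative fall in variance = r² × (0.842 × 0.350 + 0.350²) = r² × 0.417. With r = 0.7 this is 0.49 × 0.417 = 20%.

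*Odds of leaving double per point of worsening.* Numerical integration gives 0.216 in place of 0.350 and 0.17 in place of 0.417. With r = 0.7 the bias is -0.30 and the variance falls by 8%.

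| r | Bias in mean, points | Fall in variance |
|---|---|---|
| 0.5 | -0.22 to -0.35 | 4% to 10% |
| 0.7 | -0.30 to -0.49 | 8% to 20% |
| 0.9 | -0.39 to -0.63 | 14% to 34% |

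At r = 0.7 the bias is about -0.16 to -0.27 with 10% missing and -0.44 to -0.70 with 30% missing.

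**3. Comparison with sampling error at n = 24**

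- 95% half-width for the mean: 2.07 × 2 / √24 = 0.84 points.
- 95% interval for the variance as a multiple of its estimate: 23 / 38.1 = 0.60 to 23 / 11.7 = 1.97.

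At r = 0.7 both biases lie inside these limits.

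**4. What the SD alone would do to the RCT**

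Sample size is proportional to the variance. A variance 8–20% too low means the true requirement is 1 / 0.92 = 1.09 to 1 / 0.80 = 1.25 times the calculated one.

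A separate illustration assumes completers with mean -1.0 and SD 2.0, leavers with mean +2.0 (the protocol's own worsening threshold) and the same SD within each group. With k leavers of 30 and f = k/30, the overall variance is 4 + f(1 - f) × 3².
- k = 3: 4 + 0.09 × 9 = 4.81, SD 2.19, mean -0.70.
- k = 6: 4 + 0.16 × 9 = 5.44, SD 2.33, mean -0.40.

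For a fixed target difference of 1.0 at two-sided 5% and 90% power, n per arm = 2 × (1.96 + 1.28)² × variance. This gives 85 from completers only, 102 with three leavers counted and 115 with six.

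**The case against.** The strongest reply is that a reader might infer that everyone who stops treatment because of worsening disappears. The documents do not say so. The CRPS-progression reason sits under discontinuation of the intervention, follow-up then continues by default, and diaries run to day 180. Only participants who end follow-up or stop the diary are lost. This stands and sets the limits of the point.

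Nor does the worsening vanish from the trial. Pain at days 30, 60 and 90 is summarised and plotted under the CRPS severity score and BPI, a rise of 2 points or more for over a month counts in the primary safety outcome, and reasons for non-completion are reported. This also stands, but none of it alters the day-120 change.

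A reader might see a breach of the intention-to-treat principle in protocol 14.4.1, or of section 8.5, under which "the participant will remain within the trial for the purpose of follow-up and data analysis". That goes too far: section 8.5 concerns participants given alternative treatment, and keeping people in follow-up does not oblige a descriptive summary to impute.

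A reader might also conclude that a biased mean change would lead straight to an undersized RCT. In a single arm selected for high baseline pain, the mean change includes regression to the mean and placebo response. It is not a treatment difference, and the documents do not say it will be used as one. The argument is firmer for the SD.

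Finally, the direction is assumed. Protocol 10.9 also lists toxicity, intercurrent illness, pregnancy and non-adherence; losses unrelated to pain would cause no such bias.

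**Conclusion.** The point holds as a modest gap. The final pain-change summary omits participants without diary data in days 93–120, the protocol foresees a pain-related route to that state, and collected scores that could show its effect are not used. If leavers worsened, the mean is too favourable and the SD probably too small.

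The size cannot be settled from the documents. About -0.3 to -0.5 points and 8–20% of the variance follow only from the assumed SD of 2, correlation of 0.7, 20% missing and worsening-related dropout, and they lie within sampling error at n = 24. Progression item 4 tolerates up to 50% not completing treatment, but that is not a figure for missing pain data and should not be read as one.

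The complete-case summary is not invalid and need not be replaced. A model on visit scores as the main estimate would change the diary-based endpoint and is debatable with 30 participants. A supplementary analysis is justified because it is cheap and lets the RCT planners see how far the result depends on who stayed.

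**What to change.** Keep the complete-case diary summary as the main descriptive result. In SAP 25.2.3.2.1.2 add:

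- (a) For each participant without days 93–120 data, the last available NRS and its change from baseline, grouped by reason for leaving. For full withdrawals, protocol 10.9 lists only adverse events and medication use, so the last score may have to come from the weekly diary or the preceding contact.
- (b) A supplementary sensitivity estimate of the mean change and SD that includes these participants and uses the weekly diary and contact scores already collected. A parsimonious random-slope mixed model would do, with a last-observed-value or worsening scenario beside it.

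State there how partial diaries within the window are counted, so that the group in (a) is defined.

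In SAP 25.2.3.2.3.2 add:

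- (c) Global impression over all dosed participants with a 'discontinued / not assessed' row.

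The cost is some SAP text and a little programming, with no new data. The mixed model assumes missing at random in a small sample, and participants with no post-baseline score still contribute little. That is why (b) is supplementary and is shown with a worsening scenario.
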